2.3.1 Risk assessment

Expected adverse drug reactions (ADR) for BNT111 are fever, chills, lymphopenia, increase of cytokines and dizziness, not considered to have a significant impact on the risk-benefit profile of the product. NCI-CTCAE Grade 2 or 3 hypotension was seen in 8% of patients within 4 to 6 h after BNT111 administration, typically after the first or second vaccination, and patients with hypotension responded well to fluids. In rare cases, more severe events of cytokine release syndrome associated with pyrexia, hypotension, and hypoxia of higher NCI-CTCAE grades occurred. The onset was sometimes sudden; vital signs should therefore be carefully monitored for 6 h after at least the first three vaccinations.

Immune-related adverse reactions can occur with cemiplimab. Most of these, including severe reactions, resolved following initiation of appropriate medical therapy or withdrawal of cemiplimab. The most common immune-related adverse reactions seen in clinical trials (591 patients) were hypothyroidism (7.1%), pneumonitis (3.7%), immune-related skin adverse reactions (2.0%), hyperthyroidism (1.9%) and hepatitis (1.9%). Adverse reactions were serious in 8.6% patients and led to permanent discontinuation of cemiplimab in 5.8% of patients. See Section 6.8.4.2 for special warnings and precautions.

BNT111 has been given in combination with anti-PD-1 therapy in the Lipo-MERIT trial, no increase of AEs for any of the components was seen for the combination therapy compared to monotherapy. Safety data from the BNT111-01 trial interim analysis was in line with that observed in the Lipo-MERIT trial (Section 5.2 of the BNT111 IB). Based on the available safety data on TESAEs and treatment-emergent deaths, no safety signal was detected which would change the safety profile or benefit/risk assessment of BNT111 established in Lipo-MERIT trial. This was supported by the outcome of all IDMC meetings that recommended to continue the trial without modification.

Page 39 of 133 Version: 7.0 Date: 09 FEB 2023

Table 1: Summary of important, potential risks and mitigation actions taken

Potential risks	Actions taken	
General safety	An IDMC manages all potential safety concerns in this trial.	
Risks related to cancer vaccine antigen targets or anti-PD-1 therapy	Patients with clinically relevant autoimmune diseases are excluded from the trial.	

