2.3.3 Risk/benefit assessment of COVID-19 vaccination

2.3.3.1 Risk assessment

BNT111

BNT111-induced adaptive immune responses are expected to be highly specific and limited to the TAAs (see Section 2.1.2). Similarly, available European and US approved COVID-19 vaccines elicit a specific response towards the selected severe acute respiratory syndrome coronavirus 2 (SARS-CoV-2) antigens. It is thought that adaptive immune responses driven by these entirely distinctive antigens (melanoma and SARS-CoV-2) should not cross-react with each other. Consequently, BNT111 administration is not expected to impact COVID-19 vaccine efficacy and vice versa.

In parallel to the activation of the adaptive immune response mechanisms, BNT111, as observed with other RNA-LPX-based cancer vaccines, also induces an innate immune response and its administration is expected to be followed by a pulsatile release of cytokines with peaks observed at approximately 6 h after dosing and values returning to baseline by 24 h or earlier. Similarly, COVID-19 vaccination is expected to trigger a transient elevation of cytokine concentration in the peripheral blood. A 7 d interval between COVID-19 and BNT111 vaccination is therefore recommended to mitigate the risk of increased, cumulative toxicity related to cytokines release.

Cemiplimab

As outlined in Section 2.1.2, cemiplimab is a high-affinity human monoclonal antibody that belongs to the class of PD-1/PD-L1 inhibitors. By targeting and binding to PD-1, cemiplimab blocks PD-1/PD-L1-mediated inhibitory signaling in helper and cytotoxic T cells, thus releasing cytotoxic T cells to target cancer cells (for more information, refer to the cemiplimab IB). This mechanism may potentially lead to breaking of peripheral tolerance towards self-antigens and induction of unwanted immune responses towards a patients' own tissues. COVID-19 vaccination induces adaptive immune responses to the selected SARS-CoV-2 antigens and has no identified cross-reactivity with human antigens. Therefore, increased autoimmune toxicity is unlikely, although clinical data is needed to support this hypothesis. The efficacy of COVID-19 vaccination is not expected to be adversely impacted by concomitant administration of PD-1 inhibitors as PD-1/PD-L1 blockade would circumvent T cell deactivation.

BNT111 and cemiplimab combination

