6.8.4 Mitigation plans for specific AEs

6.8.4.1 BNT111

It is anticipated that patients may experience AEs of flu-like symptoms following the administration of BNT111 due to its mechanism of action. This may include, but is not limited to fever, tachycardia, arthralgia, myalgia, headache, nausea, chills and rigors. Sporadically patients also experienced moderate to severe hypotension that is potentially related to the pharmacodynamic effect of BNT111. Treatment of these events is dependent on the discretion of the investigators; however, guidance for monitoring and suggestions for management are provided below.

Safety monitoring, prophylaxis, and treatment of fever and associated symptoms

- Vital signs must be monitored prior, during and after injection:
 - Within 60 min prior to first injection.
 - At 30 min, 60 min, 4 h and 6 h after last injection of BNT111 vaccine. If no Grade ≥ 2 in the first cycle (3 vaccinations), 4 h and 6 h post dose may be skipped as per investigator's discretion and as per local clinical standard practice in subsequent cycles.
 - Optional at 24 h, based on symptomatology, clinical necessity and/or local clinical standard practice.
 - Observation period should be prolonged in case of Grade ≥ 2 fever and
 Grade ≥ 2 hypotension in the first 6 h until resolution of fever to Grade ≤ 1 and full resolution of hypotension.
 - Additional time points to be added at investigator's discretion.
- If a patient develops fever of ≥ 38°C after the administration of the BNT111 vaccine (during the observation period), secondary prophylactic pre-treatment with paracetamol and/or NSAIDs prior to all further vaccination cycles is recommended, at least 60 min before BNT111 vaccine administration followed by a second dose 2 to 8 h after BNT111 vaccine.
- Corticosteroid should be avoided as either prophylaxis or treatment as it counteracts the pharmacodynamic effects of BNT111 vaccine.

Page 65 of 133 Version: 7.0 Date: 09 FEB 2023

Table 4: Recommendations for dose modifications in case of fever

NCI-CTCAE v5.0	Guidance
Grade 1 (38 to 39°C)	Consider usage of physical/clinical methods to reduce fever (e.g., ice packs, blankets and fluids).
,	Treat with antipyretics and pretreat with antipyretics at next vaccinations.
	No change in dose.
	If AE occurs before C1D8 or for the add-on therapy before AOC1D8, the dose may be increased to CCI µg total RNA.

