Abbreviations: IV = intravenous; NCI-CTCAE v5.0 = National Cancer Institute Common Terminology Criteria for Adverse Events. Version 5.0.

Safety monitoring, prophylaxis and treatment of hypotension

- Vital signs are monitored prior, during and after injection:
 - Within 60 min prior to first injection.
 - At 30 min, 60 min, 4 h, and 6 h after last injection of BNT111 vaccine. If no hypotension in the first cycle (3 vaccinations), 4 h and 6 h post dose may be skipped at investigator's discretion and as per local clinical standard practice.
 - Observation period should be prolonged in case of Grade ≥ 2 hypotension in the first 6 h until full resolution.
 - Optional at 24 h, based on symptomatology, clinical necessity and/or local clinical standard practice.
 - Additional time points to be added at investigator's discretion.
- Ensure adequate hydration of patients on the day of trial drug administration.
- For patients taking more than one anti-hypertensive, the shorter-acting one(s) may be omitted on the day of injection.
- For patients taking one anti-hypertensive, consider omitting the dose on day of injection or during trial duration if prior event of hypotension has occurred.
- For any patient who experienced Grade ≥ 2 hypotension with prior dose of trial drug:
 - Administer IV isotonic fluid (e.g., normal saline, 500 to 1000 mL) approximately
 2 h following trial drug injections per institutional standards.
- For any patient who experienced Grade ≥ 3 hypotension with prior dose of trial drug:

Page 67 of 133 Version: 7.0 Date: 09 FEB 2023

- Consider holding or modifying anti-hypertensive medication as per investigator discretion on the day of trial drug injection and consider seeking recommendations from a cardiologist regarding anti-hypertensive medication.
- Administer IV isotonic fluid (e.g., normal saline, 500 to 1000 mL) and/or balanced crystalloid fluids approximately 2 h following trial drug injections per institutional standards.

Table 6: Recommendations for dose modifications in case of hypotension

NCI-CTCAE v5.0	Guidance	
Grade 1 Asymptomatic, intervention not indicated	No intervention.	

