The key principles of these recommendations are to maintain the comfort of the patient by management of infusion-related AEs experienced by other patients through:

- Effective prophylaxis and management of nausea and vomiting to support the patient's hydration status.
- Rapid administration of an appropriate amount of fluids.
- Keep the patient warm.
- Maintain organ function such as blood pressure, cognitive function and urinary output.
- Close monitoring of cardiac and other organ function as guided by comorbidities.
- Clinical pictures may vary, and recommendations do not replace medical reason.
- Keep other causes for symptoms in mind.

Table 7: Recommendations for management of infusion-related reactions related to trial drug

NCI-CTCAE v5.0	Guidance
Grade 1 or 2	 Treat symptomatically as indicated, including antipyretics, antihistamines, and/or analgesics as needed.
	Treat fever and neutropenia if present.
	Monitor fluid balance; administer IV fluids as clinically indicated.
	Observe patients for at least 4 h.
	Continue next dose at the same dose level.
	 For subsequent dosing, consider to use pre-medication as prophylaxis as per local clinical practice. Corticosteroids should be avoided if possible as they may counteract the pharmacodynamic effects of BNT111.
Grade 3	Withhold further treatment with trial drugs that day.
	 Strongly consider cardiopulmonary and organ function monitoring in an Intensive Care Unit.
	• Closely monitor and maintain fluid balance; administer IV fluids as clinically indicated.
	Oxygen for hypoxia.
	Vasopressor support for hypotension refractory to IV fluids.

Clinical Trial Protocol BNT111-01

Page 69 of 133 Version: 7.0 Date: 09 FEB 2023

NCI-CTCAE v5.0 Guidance

- Other supportive care as clinically indicated (e.g., fever and neutropenia, infection).
- Consider administration of corticosteroids (e.g., methylprednisolone or dexamethasone), in addition to antihistamines, antipyretics.
- May receive the next dose of trial treatment if symptoms resolve to Grade ≤ 1 for three consecutive days with approval of the medical monitor.
- For subsequent dosing consider to resume treatment with reduced dose.
- For subsequent dosing, use pre-medication as prophylaxis as per local clinical practice. Corticosteroids should be avoided if possible as they may counteract the pharmacodynamic effects of BNT111 vaccine.

Grade 4

- · Cardiopulmonary and organ function monitoring in Intensive Care Unit.

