8.2.3 Vital signs

Body temperature, pulse rate, respiratory rate, and blood pressure will be assessed at the times given in the SoA (Section 1.3).

All patients will be observed for at least 6 h after the first three administrations of BNT111 and the first administration of cemiplimab. A decision on a possible extension of the observation time to 24 h will be made at the discretion of the investigator at time of discharge.

In case a given patient tolerated the administration of the trial treatment without occurrence of significant inflammatory ADRs during the first three vaccinations (or during the next treatment cycle) of BNT111, an observation period of 2 to 4 h is acceptable at the discretion of the investigator. Prior to the dismissal of the patient, vital signs should be measured. From the second administration of cemiplimab, no observation time is stipulated with reference to cemiplimab (local protocol should be followed).

Blood pressure (systolic/diastolic, in mmHg) and pulse (in bpm) measurements will be assessed while the trial patient is in a supine position/at rest. If available, a completely automated device should be used, otherwise manual techniques can be used. The same method of measurement should be used for the trial patient during the course of the trial.

Blood pressure and pulse measurements should be preceded by at least 5 min of rest for the trial patient in a quiet setting without distractions (e.g., television, cell phones).

Vital signs to be taken before blood collection for laboratory tests.

Abnormalities observed at screening/baseline should be reported in the General Medical History. New or worsened clinically significant abnormalities observed at subsequent visits should be recorded in the AE eCRF.

Page 81 of 133 Version: 7.0 Date: 09 FEB 2023

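### From the fourth BNT111 dose, Protocol 8.2.3 and the lists in 6.8.4.1 set different conditions for relaxing post-dose monitoring, so a patient may be discharged before readings that are still due

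*Protocol*

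**What the plan says.** Protocol 8.2.3 fixes the starting rule: "All patients will be observed for at least 6 h after the first three administrations of BNT111". It then relaxes it. If the patient tolerated treatment "without occurrence of significant inflammatory ADRs during the first three vaccinations", with a bracketed phrase offering the following treatment cycle as an alternative, then "an observation period of 2 to 4 h is acceptable at the discretion of the investigator". Vital signs must be taken before the patient leaves.

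Protocol 6.8.4.1 schedules vital signs at 30 min, 60 min, 4 h and 6 h and says three times when the last two may be dropped, each time at the investigator's discretion and according to local practice:

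- Fever list: "If no Grade ≥ 2 in the first cycle (3 vaccinations), 4 h and 6 h post dose may be skipped". The kind of event is not named.
- Hypotension list: "If no hypotension in the first cycle (3 vaccinations), 4 h and 6 h post dose may be skipped". No grade is given, so any grade counts.
- Infusion-related reaction list: the same two readings may be dropped if there was no such reaction in the first cycle, again with no grade.

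The Schedule of Activities refers to both sections. The vital-sign footnotes (SOA1 footnote n, SOA2 footnote j) refer to 8.2.3 for reducing the time points. The BNT111 dosing footnotes (SOA1 footnote w, SOA2 footnote r) refer to 6.8.4.1 for the observation time.

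**The concern.** These rules control one practical decision: how long a patient stays after a BNT111 dose once Cycle 1 is over. They differ in the event that counts, the grade at which it counts and the period looked back over. Two sites that both follow the protocol can therefore treat the same patient differently, and one of them will release the patient before readings that another section keeps in force.

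Two things are at stake. One is patient monitoring: Protocol 2.3.3.1 describes a "pulsatile release of cytokines with peaks observed at approximately 6 h after dosing", so the hour at which a patient leaves is not a minor detail. The other is data. Changes in vital signs are a secondary safety endpoint, and SAP 8.5.4 summarizes the change from the pre-dose value to each post-dose time point within a visit. That summary uses the 4 h and 6 h readings.

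**Working it through.** No sample size, error rate or event count enters here, so the check is to set the rules side by side and apply each to one patient.

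| Source | What is relaxed | Condition | Look-back |
|---|---|---|---|
| 6.8.4.1, fever | 4 h and 6 h vital signs | No Grade 2 or higher event, type not named | First cycle |
| 6.8.4.1, hypotension | 4 h and 6 h vital signs | No hypotension, any grade | First cycle |
| 6.8.4.1, infusion-related reaction | 4 h and 6 h vital signs | No such reaction, any grade | First cycle |
| 8.2.3 | Stay cut to 2 to 4 h | No significant inflammatory reaction, not defined or graded | First three vaccinations, or the next treatment cycle |

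**Test case.** Grade 1 hypotension in Cycle 1 and no other event; the patient now receives the fourth vaccination (Cycle 2 Day 1).

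1. Fever list: there was no Grade 2 or higher event, so the 4 h and 6 h readings may be skipped.
2. Hypotension list: hypotension occurred, so the waiver is not met and both readings remain due.
3. Section 8.2.3: Table 6 describes Grade 1 hypotension as free of symptoms and needing no intervention. An investigator may reasonably judge it not significant, and a stay of 2 to 4 h is then allowed.
4. A patient discharged at 2 h misses both readings. One discharged at 4 h can have the 4 h reading but misses the 6 h one. Results 2 and 3 cannot both be carried out.

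**Look-back.** Take a patient who reacted in Cycle 1 and had a clean Cycle 2. The bracketed phrase in 8.2.3 can be read to let this patient qualify for the shorter stay. The lists in 6.8.4.1 look only at the first cycle and contain no such route.

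**Does the schedule settle it?** No. Section 8.2.3 gives lengths of stay and refers back to the schedule for the times of vital signs, yet the schedule cites 8.2.3 for reducing those times. Section 6.8.4.1 contains the waivers for the vital-sign times, yet the schedule cites it for observation. Neither section is said to prevail.

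**Cytokine sample.** SOA1 footnote ff requires blood before BNT111 and again 4 to 6 h afterwards in all Arm 1 and Arm 2 patients. The grid places this on Day 1 of Cycles 1, 2 and 3. Cycle 2 Day 1 is the fourth vaccination, the first at which the shorter stay is available. A stay under 4 h cannot include the post-dose sample on that day or on Cycle 3 Day 1.

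**The case against.** The strongest reply is that the three lists sit under separate symptom headings and each grants only a permission. Read together, a patient would have to satisfy every list, so the fever waiver would not override the hypotension condition. That is a natural reading, and it would remove the conflict between results 1 and 2. But no section states it, and it would leave the conflict with 8.2.3 in place, because 8.2.3 uses a different test and a different look-back.

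It can also be said that 6.8.4.1 is introduced as guidance, and that the vital-sign footnotes point to 8.2.3 as the governing text. The first is true, although the fever list itself makes vital-sign monitoring mandatory. The second is weakened by the dosing footnotes, which point the other way.

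The 2 h discharge is optional, depends on the investigator's view of what is significant, and is not practicable on the cytokine sampling days. All of that stands. It narrows how often the conflict will occur but does not resolve it.

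Finally, a reader might infer that missing 4 h and 6 h data are wholly due to the mismatch. They are not. All three lists leave skipping to discretion and local practice, so a single criterion that kept this discretion would still leave some readings missing. The by-visit change from baseline in SAP 8.5.4 uses pre-dose values and is unaffected.

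**Conclusion.** The protocol contradicts itself on when monitoring may be relaxed after the first three BNT111 doses. For the test patient, one section allows a 2 h stay while another keeps a 6 h reading due. This rests on three things: the investigator may judge Grade 1 hypotension not significant, the bracketed phrase in 8.2.3 is an alternative look-back, and no rule of precedence exists elsewhere in the documents. The conflict does not touch Cycle 1, where 6 h applies to everyone. The documents give no rate for Grade 1 hypotension, so the number affected cannot be given. It is a wording defect that should be corrected because it bears on patient safety.

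Three stronger inferences are not supported.

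- **Table 7.** For a Grade 1 or 2 infusion-related reaction it says "Observe patients for at least 4 h". A reader might set this against the 6 h rule, but both are minimums and a 6 h stay meets both.
- **Onset window.** Section 2.3.1 says "NCI-CTCAE Grade 2 or 3 hypotension was seen in 8% of patients within 4 to 6 h after BNT111 administration". This might be taken to mean that events start at 4 h, so that an earlier discharge always precedes them. The wording gives an upper limit, and Section 2.1.2 places the same 8% in the first hours after vaccination.
- **Number of patients.** Applying 8% to the 90 + 45 = 135 patients randomized to BNT111 gives 0.08 × 135 = 10.8, or about 11. That counts Grade 2 or 3 events, which Section 2.3.1 says typically follow the first or second vaccination, when the 6 h rule already binds. It does not measure this conflict.

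**What to change.** Reconcile Protocol 8.2.3, the three vital-sign lists in 6.8.4.1 and the Schedule of Activities footnotes (SOA1 n and w; SOA2 j and r):

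- Use one set of event types, grades and look-back period wherever monitoring may be relaxed. Name the event in the fever list and define the term used in 8.2.3.
- State how the lists combine and which section governs.
- Make the permitted discharge time consistent with the vital-sign readings and cytokine samples still required at that visit.

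Which criterion applies is for the sponsor to decide. The cost is protocol wording and a memo to sites, with no new assessment. The drawback is that some patients at some sites may stay longer than they do now.

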8.2.4 Electrocardiograms

Single 12-lead electrocardiograms (ECG) will be obtained as outlined in the respective SoAs using an ECG machine that automatically calculates the heart rate and measures PR, QRS, QT, and QTc (F) (QT interval corrected for heart rate according to the Fridericia formula) intervals.

The investigator must review the ECG, document this review, and record any clinically relevant changes occurring during the trial in the AE section of the eCRF.

8.2.5 Safety laboratory assessments

See Section 10.2 for the list of safety laboratory assessments to be performed and to the SoA (Section 1.3) for the timing and frequency.

All clinical laboratory assessments will be analyzed centrally at the time points outlined in the respective SoAs. Local assessments will be carried out in order to make a decision on the dosing and as otherwise specified in the SoAs (Section 1.3). Centrally analyzed screening laboratory results must be obtained within 10 d prior to initiation of trial treatment, if not otherwise specified.

The investigator must review the laboratory report, document this review, and record any clinically relevant changes occurring during the trial in the AE section of the eCRF. The laboratory reports must be filed with the source documents. Clinically significant abnormal laboratory findings are those which are not associated with the underlying disease, unless judged by the investigator to be more severe than expected for the patient's condition.

All laboratory tests with values considered clinically significantly abnormal during participation in the trial or within 90 days after the last dose of trial intervention should be repeated until the values return to normal or baseline or are no longer considered clinically significant by the investigator or the sponsor's medical monitor. Unscheduled laboratory tests can be done locally, or sent to the central laboratory.

If such values do not return to normal/baseline within a period of time judged reasonable by the investigator, the etiology should be identified, and the sponsor notified.

All protocol-required laboratory assessments, as defined in Section 10.2, must be conducted in accordance with the laboratory manual and the SoA.

If local laboratory assessments require a change in patient management or are considered clinically significant by the investigator (e.g., SAE or AE or dose modification), then the results must be recorded in the eCRF. If both central and local laboratory assessments are done at the same time, the highest grade of clinically significant abnormal findings will be reported and collected in the eCRF.

